### Qualitative data analysis considerations

Following our standard practice, study tools including in depth interview guides and survey materials will be translated into isiXhosa and Afrikaans, the predominant local languages, with independent back-translation for verification. We will digitally record the IDIs and then have the recordings transcribed verbatim. The recordings will be reviewed and verified for accuracy by the interviewers. Transcripts will then be translated and key quotations back-translated to verify meaning. A subset of 20% of transcripts will be double-coded to examine the inter-rater reliability of the coding process. After coding, Investigators will search by substantive codes and themes identified utilizing matrices to organize and allow for comparisons by group (e.g. age,

pregnancy stage, partner status, initiators and non-initiators). Patterns in the matrices will be used to identify themes. Tables of themes will be created using the verbatim quotations as evidence to support the themes that serve as the primary data analyses approach. Conclusions will be based on interpretation of these tables of themes with quotations. Data will be managed using NVivo Software (QSR International).

#### Data management

Data management will take place at the site following procedures established for other research protocols conducted in Gugulethu. Data collected on paper forms will be entered into a custom designed RedCap database, maintained in a firewall-protected UCT server with nightly backups. The study database will be password-protected following standard password safety procedures. The database will be designed and maintained by a senior data manager who will develop the data dictionary, direct queries, and data quality assurance / quality control activities, and will supervise the data entry clerk. Data quality assurance will be in the form of robust database structure and platform, and “front-end” data checks, including real-time database queries. Quality control will be through data checking scripts to identify out-of-range values, logic violations, and missing observations. Data editing will be based on reference to the form and/or source document in question; all data queries and responses will be logged, and edits will be implemented through separate program files. All study records will contain anonymous participant identification numbers, and no participant names or identifiers will be recorded. Patient routine folder numbers will be stored in a separate password protected database. Once all routine data are linked the folder number will be removed and only the study identification number will be used.

## **7. Ethical considerations**

#### Ethical review

The study protocol, informed consent form, all data collection tools, and other requested documents will be reviewed and approved by the University of Cape Town Faculty of Health Sciences Human Research Ethics Committee (UCT-HREC). After the initial review and approval, UCT-HREC will review progress of the study at least annually. Following the approval, we will submit the protocol and approval to University of California Los Angeles (UCLA) for secondary review and approval. UCLA IRB will also review progress of the study annually and we will report all adverse events or amendments to both Ethics Committees.

#### Insurance

**Currently we propose that this protocol is covered by UCT’s no-fault insurance policy as this is non-commercially sponsored interventional research.**

#### Ethics approach for including adolescent girls (16+ years old) in study

As per the Department of Health. Guidelines for Good Practice in the Conduct of Clinical Trials with Human Participants in South Africa [21] we will collect parental or guardian consent to participate in the study as well as assent from the minor.

The risk is justified by the anticipated benefit to the subjects: the risks associated with PrEP-PP study procedures are minor and largely non-invasive (except for phlebotomy) and are justified by the anticipated benefit that PrEP would have on prevention of HIV acquisition in this vulnerable group. Thus, there is the potential for direct benefit associated with participation.

## Informed consent

Our study will have two consent forms.

1. The first would be for screening and would include the consenting for the screening survey (inclusion criteria questionnaire) and consenting for the HIV testing (using antigen/antibody testing to screen for acute HIV infection) and hepatitis B surface antigen testing. The study consent form will be for enrolled participants' consent.
2. The second is the main study ICF. The study informed consent for the study and questionnaire are modelled after that used in previous studies and will be delivered in participants' home language (isiXhosa or Afrikaans) by trained interviewers. This study ICF details the purpose of the study, study procedures, and the risks and benefits to mothers that participants may encounter at the additional study measurement visit.

Here, study staff will emphasize to participants that:

- Participation is entirely voluntary, and their choice regarding participation will in no way influence the quality of routine medical care for mothers or their infants
- Women may exit the study at any time for any reason without compromising the quality of health care received.

English versions of the informed consent documents are provided in the Appendix to this document. Translated isiXhosa and Afrikaans versions (as well as a certification of their translation and back-translation) will be submitted to the HREC before the start of the study.

## Risks

The potential risks to participants in the study include:

- Risks associated with collection of self-reported behavioural and psychosocial information, related to psychosocial distress raised by questionnaire items involving social support, mental health, or disclosure of HIV status
- Risks due to loss of confidentiality due to study procedures—for instance, in the process of data collection
- Risk associated with asking participants to disclose their status, and potential for interpersonal violence by the partner resultant from the disclosure.

The potential risks to participants who take PrEP include:

- Risks associated with PrEP side effects (headaches, gastro-intestinal) for women on PrEP
- Risks associated with PrEP adverse events for women on PrEP
- Risks associated with collection of dried blood spots

All participants will be informed of these risks, and the strategies to minimize these, as part of the informed consent process. These strategies draw directly from prior experiences conducting research on HIV prevention and treatment in Gugulethu, Hanover Park and similar communities across Cape Town.

## **Benefits**

### ***Direct benefit***

The major potential direct benefit from participating in this study is that pregnant women will receive best possible HIV prevention including ongoing counseling, Hepatitis B screening, STI testing and treatment and PrEP if they choose to take it which can prevent HIV acquisition during pregnancy and breastfeeding periods. If women do not opt to take PrEP, or are not adherent to PrEP, she will still receive the ongoing counseling and STI testing. Their participation may help us answer our research questions and help us inform health programs for pregnant women in the future. The benefit of participating in the study and preventing HIV acquisition and onward infant transmission is likely to outweigh the risk of PrEP exposure or other risks.

### ***Indirect benefit***

By identifying the optimal strategy for delivering PrEP to pregnant women, this study has the potential to lead to improved HIV prevention interventions to protect against HIV acquisition and vertical transmission in HIV-uninfected women and their infants in Cape Town, the Western Cape Province, and across South Africa.

## **Compensation**

Participants will be given up to R250 in grocery vouchers for their time and effort in every study measurement visit as well as additional money to cover the cost of transport for each study visit. This is in line with ongoing research in the two sites, as the study visits will correspond to regular ANC or postpartum/well-baby clinical visits wherever possible. All participants will also receive refreshment on the day of their visit.

## **Confidentiality**

The following steps will be taken to minimize the risk of any loss of confidentiality throughout study design and conduct.

- All personnel involved in data collection and management will undergo specific training for the study in confidentiality and related patient protection issues.
- Following standard practice, all patient- and study-related information will be kept in locked cabinets at either the study office in Gugulethu, Hanover Park or at UCT.
- Anonymous participant identification numbers will be used on all study documents. Collection of participant names and other identifiers will be restricted to informed consent documents, patient tracing materials, and a study identification key, all of which will be kept in a locked cabinet in the study office at Gugulethu and at UCT separate from other study documentation and accessible only by the project coordinator and local PI. No CRF will include participant name, including CRF that may reflect HIV status of women or their children (including STI test results or treatment).
- All electronic records will be kept in password-protected files. All electronic communications of study data will be through password-protected, encrypted files. All data storage at the University of Cape Town will be within a firewall-protected server.
- The metagenomic sequencing and relevant metadata will need to be deposited into a database such as dbGaP after our publication. We will remove any identifying information from this data, including date of birth and leave age in days only.

**While efforts will be made to minimize the loss of confidentiality, in the event that staff learn that the participant is a threat to themselves or to others or of possible abuse by partners, the proper authorities will be notified. This exception will be included in all study informed consent forms.**

### **Internal monitoring**

**The purpose of monitoring is to verify the rights and well-being of human subjects are protected; that trial data is accurate, complete and verifiable with source data; that the trial is conducted in compliance with the protocol, GCP and the applicable regulatory requirements. Throughout the conduct of the study, internal study monitoring will be led by the study PIs. We are collaborating with the study Paediatrician, [name] and Obstetrician, [name], who will monitor emergent clinical concerns as co-Investigators. They will monitor all adverse events and advise on treatment for all participants who have adverse events.**

**Throughout the duration of the study, study PIs, co-investigators and the study coordinator will participate in weekly conference calls to monitor the rate of participant enrolment and the integrity of protocol implementation (including the completion of informed consent and quality of study measures). In addition, participant retention and safety endpoints will be discussed as well. We will report all serious maternal and/or infant adverse events, including any laboratory or other measures that require women to stop PrEP, to the study's DSMB and Ethics Committee.**

Because of the vulnerable nature of the study population –pregnant women and adolescent girls –, and the innovative nature of providing PrEP to those women, we have chosen to invite an independent DSMB to review study progress. While independent DSMB review is not common in implementation research, we feel that external review of study progress will be critical to maximizing the benefits and minimizing the risks of the PrEP-PP evaluation. Briefly, the DSMB will monitor:

- **Study protocol and tools for data collection**
- **The rate of recruitment at different time points**
- **Adverse events, including social adverse events, identified during the study**
- **any missing or spurious data with the Investigator, which should be resolved in a timely manner.**

### **Use of Information and Publications**

Publication or presentation of the results of this study will be agreed upon in collaboration with the study investigators. Note that the funding agency has no input in the decision to present or publish study data or the nature of the data that are presented or published.

## 1. Review of statistical design

Our study, PrEP-PP (PrEP in Pregnant and Postpartum women) will determine the distribution of women across the PrEP cascade (i.e. PrEP initiation, continuation and persistence) in a cohort of 1200 HIV-negative pregnant and breastfeeding adolescent girls and women recruited and followed in two public health facilities in South Africa to inform policymakers about the effectiveness of PrEP integration into antenatal (ANC) and postnatal care in high HIV incidence communities.

### The objectives of the study are to:

**AIM 1:** Determine the distribution of women across the PrEP cascade (initiation, continuation and persistence on PrEP) and outcomes (maternal HIV incidence, infant HIV incidence, and adverse events) in a cohort of pregnant and breastfeeding women using quantitative and qualitative approaches

- (1) Determine the distribution of women across the PrEP cascade and outcomes including HIV acquisition (maternal and infant) and adverse events
  1. PrEP initiation: defined PrEP start at any time point in the study
  2. PrEP continuation: defined as return to clinic and PrEP refill within 45 days post initiation
  3. PrEP persistence: defined as reporting taking PrEP in  $\geq 5$  out of last 7 days or  $\geq 25$  out of last 30 days (self-reported), or  $\geq 600$  fmol/punch from DBS TDF-DP (objective report)
- (2) Evaluate key predictors of PrEP initiation, continuation and persistence on PrEP including age, substance use, relationship status and partner's serostatus

**AIM 2:** Evaluate patient and provider-level factors associated with the PrEP cascade using quantitative and qualitative approaches

- (1) Evaluate individual-level factors (including risk perception, substance use, sexual activity, and partner/family/community encouragement) associated with PrEP initiation, continuation and persistence on PrEP
- (2) Evaluate pill and study factors (including PrEP-related side effects, time to participate in study, participant-provider communication) associated with PrEP initiation, continuation, and persistence on PrEP
- (3) Evaluate disease factors (including partner's HIV status, HIV-related stigma) associated with PrEP initiation, continuation, and persistence on PrEP

**AIM 3:** Apply an established mathematical model to simulate the impact of improvement in the PrEP cascade on HIV infections averted (maternal and perinatal)

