## Sample size considerations

The projected sample size for the study is *1200 women enrolled from 1st ANC visit until 12-months postpartum (estimated mean of 18-months follow-up)*. This estimate is based on the following assumptions:

- (1) 60% of women will initiate PrEP during the study period (versus approximately 40% who will not);
- (2) Approximately 75% of women on PrEP will be retained in care at 12-months (defined as not missing >1 study visit among women on PrEP)
- (3) 70% of those retained in care (n=378) will adhere to PrEP during at-risk periods.

A sample size of 1200 women yields 80% power to detect identify a relative risk of 2.0 or greater in key covariates including age (<25 vs. >25 years), pregnancy and relationship status associated with PrEP initiation versus non-initiation. A sample size of 378 women (e.g. 70% of women retained in the study on PrEP will be adherent as measured by TDF-DP measures) yields 80% power to detect relative risks of 2.0 or greater associated with persistence in the cohort. The analysis will be based on women who complete the 12-month postpartum cohort follow up. We will use relative risk ratios performed at a two-sided  $\alpha$  level of 0.05.

## Statistical analysis considerations for AIMS 1 & 2

The primary analysis for *Aim 1* will focus on measuring the distribution of women across the PrEP cascade including: initiation, continuation and persistence. **PrEP initiation** will be based on a woman's uptake of PrEP and allow for stoppage and re-initiation; **PrEP continuation** will be defined as not missing >1 visit among those on PrEP (with separate analyses of PrEP stoppage). For **PrEP persistence** for women on PrEP we will measure both *perfect persistence* (i.e. level of objective persistence throughout pregnancy and breastfeeding periods) as well as "*prevention-effective*" persistence (i.e. persistence during times of sexual activity) in participants through objective and subjective measures to evaluate agreement between the two measures, and the level of under- or over-reporting. Primary persistence analyses will use objective measures (TDF-DP from DBS) taken on all those who enrolled and initiated PrEP; subsidiary analyses will consider (i) other persistence measures and (ii) multiple imputation for missing persistence data.

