To address *Aims 1 and 2*, the modelling approach will vary depending on the nature of the outcome. PrEP initiation will be modelled using a probit model (preferred to estimate risk factors for common outcomes) with individual-level covariates as fixed effects; when time-dependent or visit-specific covariates are included in the analysis of cumulative initiation (for *Aim 2*) we will shift to a mixed-effects setting with random effects around individual participants. PrEP continuation will be examined using similar approaches; in addition, we will use time-to-event methods to estimate factors associated with time to loss (non-continuation) among women having initiated PrEP. PrEP persistence will be modelled using mixed effects probit models as above and generalized estimating equations to examine the marginal effect of individual-level covariates on persistence during the study. Throughout, robust estimates of standard errors will be used.

For each outcome, covariates in the multivariable models will be selected a priori using directed acyclic graphs; the main exposures of interest include: age (<25 vs. >25 years old), pregnancy status (by trimester and pregnant vs. postpartum), relationship status (married/cohabiting vs. not) and substance use (vs. none). We will explore associations within subgroups of participants using interaction terms in predicting outcomes involving these four covariates in particular. Throughout the analysis of outcomes in the PrEP cascade, losses of patients at early stages are highly informative about outcomes later in the cascade. To specifically address this, we will perform further bias analyses with inverse probability of censoring weighting in addition to complete case analyses. We will also use multiple imputation via chained equations for missing data [83] to examine the potential impact of missing data.

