**Table 1. Study measures for PrEP-PP for AIM 1**

Primary Outcomes	Measurement	Source	Frequency
PrEP initiation	# of women who initiate PrEP over time / total # of women in active cohort = proportion of women who initiate PrEP	Electronic provider log (REDCap)	Quarterly
PrEP continuation	# of women on PrEP who return for study visits (do not miss more than 1 visit) / total # of women in active cohort who are prescribed PrEP= proportion of women on PrEP who continue in PrEP study	Electronic provider log (REDCap)	Quarterly
PrEP persistence (subjective)	# of women reporting taking PrEP in $\geq 5$ out of last 7 days or $\geq 25$ out of last 30 days (self-reported)/ total woman-time on PrEP in active cohort = PrEP persistence rate (subjective)	Electronic provider log (REDCap)	Quarterly
PrEP persistence (objective)	# of women taking PrEP who have $\geq 600$ fmol/punch (~7 doses/week) from DBS TDF-DP at 3rd trimester, delivery, and 6 weeks postpartum (and during sexual risk periods during that time) / total woman-time on PrEP in active cohort = PrEP persistence rate (objective)	Lab analysis of TDF-DP measures	Yearly and end of study
Secondary Outcomes			
Prevention effective persistence	4. # of women reporting adherence to PrEP (as per PrEP persistence subjective measure)/ total woman-time reporting sexual activity in past 30 days	Electronic provider log (REDCap)	Quarterly
	5. # of women having TDF-DP in DBS (as per PrEP persistence objective measure)/ total woman-time reporting sexual activity in past 30 days	Lab analysis of TDF-DP measures	Yearly and end of study

Prevention effective continuation	# of women who don't miss any PrEP study visits/ total woman time reporting sexual activity in prior visit	Electronic provider log (REDCap)	Quarterly
Predictors of attrition at key steps in the PrEP cascade	Individual, pill/study and disease specific predictors of PrEP initiation, continuation and persistence	Study CRFs and in-depth interviews (month 7 and12) (mixed methods)	End of study
Healthcare provider attitudes and knowledge about PrEP in pregnancy	Provider knowledge about PrEP and barriers/facilitators to PrEP prescription in ante and postnatal care	In-depth interviews	Year 1 of study
HIV outcomes	HIV testing data: HIV-uninfected, HIV incidence in mother and child (if mother seroconverts) compared by PrEP use/non-use	Electronic provider log (REDCap)	End of study

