#### ***Methods/Approach:***

- (1) Study flow figure (see Continuation Flowcharts)
- (2) Number screened per week and month (target= 18 per week, 72 per month) vs number enrolled
  - a. The projected sample size for the study is 1200 women enrolled until 12-months postpartum (estimated mean of 18-months follow-up).
- (3) Subjects initiating PrEP compared to those who do not
  - a. Estimated that 60% of women (n=720) will initiate PrEP during the study period (versus approximately 40% who will not).
- (4) Continuation and persistence by group
  - a. Assumed that approximately 75% of women on PrEP (n=540) will continue on PrEP at 12-months (defined as not missing >1 study visit among women on PrEP);
  - b. Assumed that 70% of those retained in care (n=378) will adhere to PrEP during at-risk periods.
- (5) Final completion rates
  - a. Compare final number of participants who enroll in study, who initiate PrEP, who are retained in care, and who adhere to PrEP to sample sizes needed to yield 80% power (i.e., n=1200, 720, 540, 378, respectively).
- (6) Number of subjects in analysis data sets
  - a. Consider number of participants that will potentially be excluded from analyses because of withdrawal from study, missing data on key covariates or outcomes, etc.

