#### **Methods/Approach:**

- (1) **Primary outcome:** See **Table 1** for precise definitions of (1) PrEP initiation, (2) PrEP continuation, (3) PrEP persistence-subjective, and (4) PrEP persistence-objective
- (2) **Primary analysis:** Describe each outcome listed above via cumulative incidences at fixed intervals (e.g., cumulative PrEP initiation by delivery) and incidence densities over time. The general statistical approaches to these outcomes are analogous; data will be described graphically, including product-limit graphs, with preliminary analyses based on standard approaches for rates and proportions.
  - a. **PrEP initiation** will be modelled using a probit model (preferred to estimate risk factors for common outcomes) with individual-level covariates as fixed effects.
  - b. **PrEP continuation** will be examined using similar approaches; in addition, we will use time-to-event methods to estimate factors associated with time to loss (non-continuation) among women having initiated PrEP.
  - c. **PrEP persistence** will be modelled using mixed effects probit models as above and generalized estimating equations to examine the marginal effect of individual-level covariates on persistence during the study.
    - a. **Sub-group analysis:** we will analyze the primary outcomes by sub-groups including age (<25 and  $\geq$ 25 years), STI diagnosis, relationship status, pregnant/postpartum

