#### **Missing data:**

Primary persistence analyses will use objective measures (TDF-DP from DBS) taken on all those who enrolled and initiated PrEP; subsidiary analyses will consider (i) other persistence measures and (ii) multiple imputation for missing persistence data. Specify any sensitivity analyses. Specify how the impact of missing data on the primary results will be interpreted.

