**Interpretation:**

The analysis will be based on women who complete the 12-month postpartum cohort follow up. We will use relative risk ratios performed at a two-sided  $\alpha$  level of 0.05.

Summarize how the results will be interpreted. You can include what level of statistical significance will be used to determine the trial's main conclusion/recommendation. You can also describe how disagreement or coherence between primary and secondary results will be interpreted.

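### PrEP continuation carries two definitions under one name, and the SAP's completer sentence conflicts with the all-initiator denominator on which the 75% was planned

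*Combined protocol and SAP*

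**What the plan says.** **Definition.** The Aim 1 objectives in SAP section 1 give: "PrEP continuation: defined as return to clinic and PrEP refill within 45 days post initiation". The SAP's statistical considerations for Aims 1 and 2 say instead that continuation "will be defined as not missing >1 visit among those on PrEP (with separate analyses of PrEP stoppage". The missed-visit rule recurs in the SAP's study-measures list, in Table 1 (study measures for Aim 1), in section 2.2 and in the Table 2 template of section 4. Section 2.4 refers to Table 1 "for precise definitions of (1) PrEP initiation, (2) PrEP continuation".

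**Denominator.** Table 1 divides by "total # of women in active cohort who are prescribed PrEP= proportion of women on PrEP who continue in PrEP study". Section 2.2 gives the planning value: "Assumed that approximately 75% of women on PrEP (n=540) will continue on PrEP at 12-months", on 720 initiators.

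**Analysis set.** The SAP's sample-size text and the Interpretation paragraph of section 2.4 both say: "The analysis will be based on women who complete the 12-month postpartum cohort follow up". For persistence, the next cascade step, the Missing data paragraph of section 2.4 names objective measures "taken on all those who enrolled and initiated PrEP". No matching statement is made for continuation.

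**Loss.** Protocol section 4 lists loss to follow-up, together with seroconversion, moving away and transfer, as reasons for censoring. The SAP's modelling text and section 2.4 treat time to loss as time to non-continuation.

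**The concern.** Continuation is one of the three primary cascade steps meant to inform policymakers, and protocol section 6 plans to feed cohort results on the cascade, retention included, into the Aim 3 model.

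The two definitions differ in time point (day 45 against follow-up to 12 months) and in event (a refill against attendance). They can classify one woman in opposite ways:

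- A woman who refills on day 30 and then leaves has continued by the 45-day rule. If kept in the denominator, she has not continued by the missed-visit rule.
- A woman who misses her 1-month visit, first refills on day 50 and attends every visit after that is the reverse. She has missed at most one visit, whether or not the 1-month visit counts.

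The completer sentence raises a different problem. Finishing 12 months of postpartum follow-up and not missing more than one visit are closely linked, so restricting to completers selects partly on the outcome being measured. A proportion among completers is not the quantity that was planned.

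**Working it through.** **1. The plan's own figures** (SAP sample-size text and section 2.2)

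- Initiators: 1200 × 0.60 = 720
- Continuing at 12 months: 720 × 0.75 = 540
- Adherent: 540 × 0.70 = 378

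All three match the stated counts. The 75% is therefore planned on all 720 initiators, with 720 − 540 = 180 not continuing.

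**2. Effect of removing women from the denominator**

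Let m be the number of initiators removed because they did not complete, and q the share of those m who met the continuation definition. The reported figure is

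(540 − mq) / (720 − m)

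The documents give neither m nor q. Assumed ranges:

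| q | m = 45 | m = 90 | m = 135 |
|---|---|---|---|
| 0 | 540/675 = 80.0% | 540/630 = 85.7% | 540/585 = 92.3% |
| 0.5 | 517.5/675 = 76.7% | 495/630 = 78.6% | 472.5/585 = 80.8% |
| 0.75 | 75.0% | 75.0% | 75.0% |
| 0.9 | 499.5/675 = 74.0% | 459/630 = 72.9% | 418.5/585 = 71.5% |

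The figure is unchanged when q equals the overall 75%, rises below that and falls above it. Untraceable women would probably have low q. Women who attended well and then moved, transferred or seroconverted could have high q.

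**3. Effect of swapping the definition**

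Let a be the share of the 540, and r the share of the 180, who refill by day 45. The 45-day figure is (540a + 180r)/720, and the two rules disagree on 540(1 − a) + 180r women. The documents give neither a nor r. Two assumed cases:

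- a = 0.9, r = 0.5: (486 + 90)/720 = 80.0%, with 54 + 90 = 144 of 720 women classified differently.
- a = 0.9, r = 0: 486/720 = 67.5%, with 54 women classified differently.

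**4. The SAP's statements on the analysis set, side by side**

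- The considerations for Aims 1 and 2 and section 2.4 describe each primary outcome by cumulative incidence at fixed intervals, incidence density and product-limit graphs. These use each woman's follow-up until she is lost.
- The completer sentence, repeated inside section 2.4, would exclude those same women.
- Protocol section 4 would censor a woman at loss, while the SAP's time-to-loss analysis would count her as an event. A product-limit curve differs according to which is followed.

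**The case against.** The case for the plan has four parts.

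- **Governing definition.** A reader might infer that the primary definition is undecided. The documents do not support that: section 2.4 points to Table 1, and the other SAP statements of the rule agree with it. What stands is a single line in the objectives, neither withdrawn nor labelled as another outcome.
- **Scope of the completer sentence.** It sits directly before the sentence on relative risks and can be read as covering only the association analyses. The stated descriptive methods favour that reading. However, the sentence carries no such limit and is repeated in the primary-analysis section.
- **Planned mitigation.** The SAP says "we will perform further bias analyses with inverse probability of censoring weighting in addition to complete case analyses", and adds multiple imputation and a time-to-loss analysis among initiators. Section 2.2 compares final counts with 720 and 540. The SAP also allows alternate definitions of the main outcomes, compared for agreement, although its example is persistence and it does not mention the 45-day rule. These provisions soften the problem, but none fixes the denominator of the primary proportion.
- **Direction.** A reader might infer that the completer rule will inflate reported continuation. The documents do not establish this: they give neither the number removed nor how many of them had continued, and the arithmetic can go either way.

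**Conclusion.** The concern holds in a limited form and should be fixed. The missed-visit definition governs the primary analysis, and the defect there is an unlabelled second measure under the same name. The completer sentence conflicts with the planned 540/720 and with the primary descriptive methods. If applied to continuation, it would replace the planned quantity with one selected on the outcome. Protocol and SAP also disagree on whether loss is censoring or non-continuation.

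The textual conflicts are certain. The size is not: 75% could become 92.3% (135 removed, none had continued) or 71.5% (135 removed, 90% had continued), and both rest on assumed inputs. They show how sensitive the figure is, not how biased it will be.

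**What to change.** 1. Keep the Table 1 missed-visit definition as the primary outcome, and rename the 45-day refill in the objectives as a separate early-continuation outcome.
2. Remove the completer restriction for continuation. Use all women who initiated PrEP as the denominator at each fixed time point.
3. Reconcile protocol section 4 with the SAP. For this outcome, count loss to follow-up and withdrawal as non-continuation from that point. Keep moving, transfer and seroconversion as censored, with a sensitivity analysis for the proportion.

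Secondary clarifications:

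- State which visits count. The 1-month visit is a study visit in protocol section 5 but a refill visit (v1.1) in the SAP templates, and visit and refill intervals vary within protocol section 5 and its Table 1. The status of a phone interview offered after a missed visit is also unstated.
- Align the loss thresholds: more than 8 weeks in protocol section 4, 90 or more days in the SAP's monthly report template.

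The cost is a few lines of SAP wording and a matching protocol clarification. No new data are needed, because attendance is in the REDCap log and the SAP already plans to use pharmacy refill records. The downside is that reported continuation may be lower.
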